4.0 Research Design and Methods

4.1 Type of Study

This is a single-site study that will take place at VA Pittsburgh Healthcare System, Pittsburgh, PA. It is a prospective randomized clinical trial evaluating the two different nerve block injection drugs for TKA and THA, introduced above and described further below. All described RegA techniques strategically avoid GETA and high-dose opioids, and the immediate postoperative complications (from GETA and high-dose opioids) that inhibit full-capacity cognitive function needed to accomplish PT/OT goals during the first 2 days after TKA/THA. Two hundred (200) total patients will be recruited and evaluated for study outcomes pre-TKA/THA (100 for TKA, 100 for THA). Following pre-surgical evaluation, patients will be block-randomized (stratified by [a] TKA vs. THA surgical procedure, [b] age, and [c] presence of diabetes). After surgery, all patients will undergo the same standardized PT/OT best-evidence care plans consistent with current clinical care at our institution. Evaluation of study outcomes will take place during the first two days after surgery, throughout the remainder of the hospital stay (which typically ranges from 2 to 5 days, including discharge day), and during the first two orthopedic post-op follow-up evaluations. The primary outcome is pain at 24 hr after surgery, and exploratory outcomes include physical therapy progress and anesthesia-related symptoms. We will also assess additional metrics of anesthesia and physical therapy success such as range of motion, physical function and performance testing, length of hospital stay, discharge placement, readmission, falls, and other adverse events.

Study Treatment Groups:

Institutional Standard of Care (ISOC)

All patients will receive a standardized bupivacaine spinal anesthetic, consistent with current institutional practice. All patients will receive pre-medications for the prevention of pain, nausea, vomiting, and gastroesophageal reflux, consistent with current institutional practice. All patients will receive intravenous hydration, intravenous antiemetics, and intravenous blood pressure support (e.g., intravenous phenylephrine bolus/infusion) consistent with our current institutional practice. The need for intraoperative blood transfusion will occur based on current institutional practice and collaborative decision-making between the surgical and anesthesia teams, consistent with current institutional practice.

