4.4 Data Collection

Primary Outcome – Pain

Pain - Pain will be measured by the Short-Form McGill Pain Questionnaire (36). (SF-MPQ, version 2) and the Defense and Veterans Pain Rating Scale (DVPRS, which entails a 0-10 numeric rating scale along with step-function visual cues, color-coded visual cues, and verbal descriptors of pain intensity). The specific aim is the 24-hour pain severity as measured by the SF-MPQ. The DVPRS will be used to assess (i) “rebound pain” for pain with movement, compared with baseline, during and after nerve block analgesic effects are experienced and (ii) “block duration” (11) for time interval between block placement and peak postoperative DVPRS score with movement.

Exploratory Outcomes – Physical Function, Other Symptoms, and Recovery from Anesthesia

Data will be recorded by the research coordinator and/or VAPHS Staff Physical Therapists and/or “without compensation” (WOC) physical therapists hired through the University of Pittsburgh specifically for the care of study patients.

Data Management System

Data management will be coordinated at VAPHS by StatCore. Data entry will be primarily performed using the VA’s REDCap software (https://vhacdweb05.vha.med.va.gov/redcap_v6.0.27/index.php?pid=1440) via laptop or desktop personal computers. Data will never reside on the data collection devices, which serve only as portals to the password protected database. Only authorized members of the study team will have access. Data will reside on the VA Informatics & Computing Infrastructure (VINCI) server – which is also password protected and independent from all other servers. Data will be downloaded from the REDCap server by StatCore for analytic and data management purposes. Downloaded data will reside on a password-protected VAPHS secure shared drive. REDCap is a secure web-based platform that can only be accessed through the VA intranet, and it is situated behind the VA firewall. Account login information is required, and then the data are stored on the REDCap server. The data to be entered (and catalogued in a detailed data dictionary) are password-protected within REDCap via login requirements, and the downloaded data are secured by permission only access to the shared drive (\\\whapthshare\Nerve_Block_Study\).

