5.0 Statistical Analysis

5.1 Analysis Plan

Data will first be assessed for outliers (+/- 2 SD from the mean) and normality. Outliers will be corrected, if possible, or dropped from the analyses. Distribution, measures of central tendency, variability, and normality will be examined. Data transformations or non-parametric techniques will be applied as needed. We will delete observations with missing values. Spearman correlation coefficients will be computed to examine associations between nerve block drug treatments, replacement surgery

type (hip versus knee), and the outcome measures (SF-MPQ, SF-8, SF- 36, WOMAC, FIM, repeated chair stand test, Opioid Symptom Distress Scale, Defense and Veterans Pain Rating Scale and its Supplemental Questions) from all time points (1 day, 2 day, 3 day, 4 day, Follow-Up Visit 1, Follow-Up Visit 2). Associations between the outcomes across time points will also be examined with Pearson (SF-MPQ, SF-8, SF-36, WOMAC, repeated chair stand test, Opioid Symptom Distress Scale) and Spearman (FIM, Defense and Veterans Pain Rating Scale and its Supplemental Questions) correlation coefficients. We will test all hypotheses and aims by conducting longitudinal multi-level modeling. The level-one unit will be the repeated measures across time, the level-two unit will be the individual patient, and the level-three unit will be nerve block type and surgical site (knee versus hip) groupings (with additional analyses involving age and diabetes status, reflecting the randomization strata). This mixed model procedure will allow the assessment of outcome and exposure variables relationships while adjusting for covariates, and separate assessments of fixed and random effects (i.e., group and individual-level data) using highly correlated repeated measures data. Covariates included in modeling will be age, diabetes status, gender, weight, smoking status, initial health status (e.g., baseline SF-8 / SF-36 and WOMAC), and concurrent general health status (e.g., daily SF-8, subsequent SF-36, and WOMAC).

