The **primary hypothesis** of an improvement in pain (measured by the SF-MPQ- version 2) 24 hr after surgery during in-hospital recovery comparing plain local anesthetics versus ISOC MMPNA will be tested using a mixed model. This procedure will test for nerve block drug treatment and surgical site (hip versus knee) effects, as well as an interaction between them. Differences in pain levels will also be examined across the study's day-of surgery, 1, 2, 3, and 4 day, and Follow-Up Visit 1 and Follow-Up Visit 2 time points. The secondary aims of short- and long-term physical therapy and rehabilitation-related benefits will also be examined for nerve block drug treatment and surgical site by a mixed model. The tertiary aim to determine differences in opioid-related side effects will use a mixed model. As with other analyses, there will be an examination for nerve block drug treatment and surgical site effects, as well as an interaction between them, along with analyses of the other randomization strata (age, diabetes) as described above.

The **exploratory aims** of physical therapy progress, return-to-home benefits, etc. will be examined using a mixed model. This procedure will test for nerve block type and surgical site effects, as well as an interaction between them. Number of days from the joint replacement procedure to the patient's home discharge will be assessed. Pain responses, as measured by the SF-MPQ – version 2, and use of postoperative opioids with additional measurement by the Opioid-Related Symptom Distress Scale will also be assessed. General health status will be evaluated with the SF-8 and SF-36. Measures of pain, analgesic side-effects, and general health status will be covariates included in the modeling of the effect of MMPNA on return-to-home.

Only after all data are analyzed and results are checked and verified by the biostatisticians will the study be unblinded.

5.2 Adverse Events. For adverse events, we will calculate cumulative probability using survival analysis techniques such as the product-limit estimator. Unlike proportions, product-limit estimators can be applied at various times following randomization, and can take into account when adverse events occur. The six-week incidence (and 95% CI) of individual adverse events by organ system and relatedness to the study will be calculated for each group. We will estimate the incidence of adverse

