5.6 Sample Size Determination

Although the SF-MPQ data is the basis of our specific aim, we do not have our own preliminary SF-MPQ data. So we will base our sample size on our most robust data, that being nerve block duration from our observational data (40 hr mean, with 14 hr standard deviation). Hip replacement and knee replacement surgery are different procedures requiring anatomically different nerve blocks as described above, so we will consider these samples as separate. We consider a doubling of the nerve block duration (15 hr for plain bupivacaine, 30 hr for bupivacaine-CBD) as a clinically significant difference with respect to the military objectives of evacuation and transport. We forecast that as a single-drug (and based on historical literature), the standard deviation of plain bupivacaine duration would be half of the 15 hr projected duration (i.e., 7.5 hr). Due to likely variability in study participant responsiveness to the 4-drug mixture, we predict that the standard deviation of the bupivacaine-CBD treatment would also be half of the projected 30 hr duration (i.e., 15 hr). We believe that the 30 (SD=15) hr duration for bupivacaine-CBD is a reasonably conservative duration based on our preliminary data of 40 (14) hr block duration. Using a 2-tailed t-test with $\alpha=0.05$, 20 patients per procedure for bupivacaine treatment, and 80 patients per bupivacaine-CBD treatment would yield 95% statistical power. This sample size will also accommodate for our multiple secondary aims. Attrition of 6 active control treatment patients ($n=14$) and of 24 MMPNA-treated patients ($n=56$) will still yield just over 80% statistical power. All calculations were performed using IBM SPSS SamplePower version 3.0.1, Chicago, IL.

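### Section 5.1 does not say how the 24 h treatment effect on SF-MPQ-2 pain is obtained from the longitudinal model, and the effects it names would give one shift pooled over visits

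*Combined protocol and SAP*

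**What the plan says.** Two sections fix the time point. Section 4.1: "The primary outcome is pain at 24 hr after surgery". Section 4.4: "The specific aim is the 24-hour pain severity as measured by the SF-MPQ". The aims in section 1.0 agree.

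Section 5.1 sets the method for everything: "We will test all hypotheses and aims by conducting longitudinal multi-level modeling". It defines the structure as "The level-one unit will be the repeated measures across time", with patients as level two and the block type and surgical site groupings as level three. The covariates include health status measured concurrently, such as the daily SF-8.

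The primary hypothesis is then described as pain "24 hr after surgery during in-hospital recovery comparing plain local anesthetics versus ISOC MMPNA will be tested using a mixed model". The next sentence names the effects: "This procedure will test for nerve block drug treatment and surgical site (hip versus knee) effects, as well as an interaction between them". After that comes "Differences in pain levels will also be examined across" the day of surgery, Days 1 to 4 and both follow-up visits, with no method given.

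The study calendar (Appendix 1) schedules SF-MPQ-2 at baseline, pre-procedure, post-procedure, Post-Op Days 1 to 5 and Follow-Up Visit 2. It marks none at Follow-Up Visit 1, although section 5.1 includes that visit in its pain comparisons.

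**The concern.** In a repeated-measures model whose only treatment terms are treatment and treatment-by-site, the treatment effect within each site is assumed to be the same at every visit. That assumption does not fit what the protocol expects. Section 2.1 gives plain bupivacaine 8-16 h. Section 2.2 reports a median of 37 h for the 4-drug block. Section 5.6 plans on a "doubling of the nerve block duration (15 hr for plain bupivacaine, 30 hr for bupivacaine-CBD", with 40 h in the sponsor's own observational data. Early after surgery both blocks should be working, at 24 h mostly the 4-drug block, and by about Day 3 neither. The difference between arms is therefore concentrated around the visit named in the specific aim.

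If the named effects are all that is fitted, the primary test answers a different question from the specific aim, with a smaller expected difference. If the analysts add something unwritten, the estimand of the primary test is settled outside the plan. Section 5.4 makes early termination depend on whether the specific aims have been met, so the interim looks need the same definition. The exploratory aims, which separate short-term from long-term benefit, have the same gap.

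**Working it through.** The plan has no figure of its own for this point. Its only power calculation (section 5.6) is a t-test on block duration, and no SF-MPQ-2 effect, SD or correlation between visits is given. The check below therefore concerns the shape of the effect over time, not its size in pain points.

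**Inputs from section 5.6.** Plain bupivacaine: mean 15 h, SD 7.5 h. 4-drug block: mean 30 h, SD 15 h (planning values), or mean 40 h, SD 14 h (observational data).

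**Assumptions.**
- Durations are normally distributed.
- The post-procedure visit is at 6 h, and Days 1 to 5 are at 24, 48, 72, 96 and 120 h. Time from block placement and time from surgery are treated as the same.
- A working block lowers mean pain by the same amount at any visit, so the arm difference in pain is proportional to the arm difference in working blocks.
- Visits have equal weight. This is what a model with one constant shift gives with complete data and equal correlation between visits.

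**Step 1. Share with a working block at time t:** 1 − Φ((t − mean)/SD).

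At 24 h:
- plain: 1 − Φ((24 − 15)/7.5) = 1 − Φ(1.20) = 0.115
- 4-drug, 30 (15) h: 1 − Φ(−0.40) = 0.655, difference 0.540
- 4-drug, 40 (14) h: 1 − Φ(−1.14) = 0.874, difference 0.758

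**Step 2. Difference between arms by visit.**

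| Visit | 4-drug 30 (15) h | 4-drug 40 (14) h |
|---|---|---|
| Post-procedure (6 h) | 0.060 | 0.107 |
| Day 1 (24 h) | 0.540 | 0.758 |
| Day 2 (48 h) | 0.115 | 0.284 |
| Day 3 (72 h) | 0.003 | 0.011 |
| Days 4, 5 and Follow-Up Visit 2 | 0 | 0 |

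**Step 3. Pooled difference as a fraction of the 24 h difference.**

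- Seven visits (post-procedure, Days 1-5, Follow-Up Visit 2): (0.060 + 0.540 + 0.115 + 0.003)/7 = 0.103, and 0.103/0.540 = 19%. For 40 (14) h: (0.107 + 0.758 + 0.284 + 0.011)/7 = 0.166, and 0.166/0.758 = 22%.
- Four visits (post-procedure, Days 1 and 2, Follow-Up Visit 2), as for a patient discharged early: 0.715/4/0.540 = 33%, and 1.149/4/0.758 = 38%.
- Three visits (post-procedure, Days 1 and 2): 0.715/3/0.540 = 44%, and 1.149/3/0.758 = 51%.
- 24 h data only: 100%, no dilution.

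The answer thus runs from about one fifth of the 24 h difference to all of it, depending on a choice that section 5.1 does not record.

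**Step 4. Does a 24 h-only model fit the text?** It fits the sentence that states the primary hypothesis. It does not fit the structure set for all hypotheses: with one outcome score per patient there are no repeated measures at level one, no separate patient-level random effect, and nothing for daily concurrent covariates to vary over. The two parts of section 5.1 point to different analyses.

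**The case against.** The strongest reply is that section 5.1 ties the mixed-model test to pain at 24 h, and that the word introducing the effects refers back to that test. The other time points come afterwards, as something examined in addition. The sentence lists effects to be tested, not every model term: it also omits the covariates given earlier in the same section, which are plainly meant to be in the model. An unnamed time term, or a 24 h-only model, is therefore compatible with it.

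Much of this stands. A reader might infer that the plan has adopted the average over all visits up to Follow-Up Visit 2 as its primary estimand. The documents do not say so; that average is what the named effects would produce if nothing else were added. A reader might also infer that a true 24 h benefit would go unnoticed. The examination across time points would probably show it, although with no stated method and outside the primary test. Nor do the documents support the idea that rebound pain on Day 2 in the 4-drug arm would cancel the benefit: section 2.2 says that longer duration appears to attenuate rebound pain.

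The 19-22% figure is the least favourable case shown. Section 4.1 gives stays of 2 to 5 days including the discharge day, so many patients will have no scores on the later days.

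What the reply does not remove is that the repeated-measures structure is prescribed for all hypotheses and that no 24 h contrast is written anywhere.

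**Conclusion.** The primary analysis is under-specified at a point that determines its estimand. Section 5.1 prescribes a longitudinal model and names treatment, site and treatment-by-site; with only those effects, the result is a pooled shift and not the 24 h effect of the specific aim. On the protocol's durations, the pooled difference in working blocks is about 19-22% of the 24 h difference over seven visits and about 44-51% over post-procedure to Day 2, with no dilution if only 24 h data are used. These fractions rest on normal durations, a 6 h post-procedure visit, equal visit weights and pain proportional to block status.

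A loss of power is tempting to quote, but any such figure needs an SF-MPQ-2 effect, SD and between-visit correlation that the documents do not give. The finding is a gap between the stated aim and the stated model, not proof that the wrong quantity will be reported.

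**What to change.** In section 5.1, state that the SF-MPQ-2 model includes visit as a categorical factor and treatment-by-visit terms. List the visits that enter it, reconciled with the calendar for Follow-Up Visit 1 and Day 5. Name the treatment contrast at the 24 h (Post-Op Day 1) visit as the primary test. Alternatively, specify a 24 h-only model adjusted for baseline SF-MPQ-2, and exempt the primary hypothesis from the rule that all hypotheses use the longitudinal model. A treatment-by-site-by-visit term is optional.

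For the exploratory aims, use the matching contrasts: in-hospital visits for short-term benefit and Follow-Up Visit 2 for long-term benefit. Use the same primary contrast at the interim looks in section 5.4.

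The cost is a few sentences and a few more model parameters. No new data are needed. The change should be dated before any comparison of outcomes by group.

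### Deleting missing values and dropping values beyond 2 SD removes the patients who get home latest from the analysis of days to home discharge

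*Combined protocol and SAP*

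**What the plan says.** Section 5.1 sets one general approach: "We will test all hypotheses and aims by conducting longitudinal multi-level modeling". It continues: "The level-one unit will be the repeated measures across time". Return-to-home is then assigned to this approach by name, since "physical therapy progress, return-to-home benefits, etc. will be examined using a mixed model". The quantity is "Number of days from the joint replacement procedure to the" patient's "home discharge will be assessed".

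Two data rules open the same section and make no exception for any outcome:

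- On missing data: "We will delete observations with missing values".
- On values more than 2 SD from the mean: "Outliers will be corrected, if possible, or dropped from the analyses".

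Section 4.1 lists among the further metrics "length of hospital stay, discharge placement, readmission, falls, and other adverse events", so discharge to somewhere other than home is foreseen. The study calendar (Appendix 1) has a row for discharge disposition, which the table marks at Follow-Up Visit 2. It has no row for a date of arrival home. Nothing says what days-to-home value is given to a patient discharged to a facility or not yet home at last contact. Section 5.2 plans product-limit estimators, but for adverse events only.

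**The concern.** Days to home is a time to an event that some patients may not have reached when last seen, and that others reach only after a stay in a facility. These are the slowest returns, and both data rules in section 5.1 act on them.

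The reason for removal is the outcome itself, so the loss costs more than precision. The arm with more slow returns loses more of them and looks better than it is. A benefit of the 4-drug block that came from fewer or shorter facility stays would be understated in this analysis. A harm of the same kind would be understated too.

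The return-to-home model also includes pain, side-effect and health-status measures as covariates. Under the same deletion rule, a missing covariate could remove further patients.

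**Working it through.** The plan states no figure for this outcome, so there is none to reproduce. Its only power calculation (section 5.6) concerns block duration and is not used here.

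**Step 1: what the rules do to a patient discharged to a facility.** There are three possibilities.

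1. No home date is obtained, or the patient is not home at last contact. The value is missing and the patient is deleted.
2. The true later date is obtained. It is set against stays of typically 2 to 5 days and is likely to exceed +2 SD. A genuine date leaves nothing to correct, so the rule drops it.
3. The date of leaving hospital for the facility is used as the home date. A transfer then counts as a return home. The plan neither states nor excludes this.

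**Step 2: a hand illustration.** All inputs except the arm sizes are assumed. Arms: 40 control and 160 MMPNA (20 and 80 per procedure, two procedures; section 4.1). Assumed: facility discharge 25% in control and 15% in MMPNA; everyone leaves hospital on day 3; facility patients reach home on day 17.

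- Control mean: 0.75 × 3 + 0.25 × 17 = 6.5 days.
- MMPNA mean: 0.85 × 3 + 0.15 × 17 = 5.1 days.
- True difference: 6.5 − 5.1 = 1.4 days.
- Facility patients deleted, or dated at transfer: 3.0 against 3.0, difference 0.
- True dates kept and the 2 SD rule applied to the pooled data: facility patients number 10 + 24 = 34 of 200, or 17%. Mean = 3 + 0.17 × 14 = 5.38. SD = 14 × √(0.17 × 0.83) = 5.26. The limit is 5.38 + 2 × 5.26 = 15.9. Day 17 lies beyond it, so all 34 are flagged and the difference is again 0.

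In this two-value setting, with facility share p and delay D, a facility patient is flagged when (1 − p)D > 2D√(p(1 − p)). This simplifies to 1 − p > 4p, or p < 20%. Below one fifth, every facility patient is flagged, whatever the delay.

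**Step 3: a simulation with varying stays and delays.** Same arm sizes, 4,000 replicates. Assumed: mean hospital stay about 3.2 days in both arms, and facility patients home 10 to 30 days after leaving hospital (mean 20). The true difference is then the difference in facility shares × 20. Entries are control minus MMPNA, in days.

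| Facility share, control / MMPNA | True difference | Facility patients deleted | Transfer date used as home date | True dates, 2 SD rule | Facility patients dropped by 2 SD rule |
|---|---|---|---|---|---|
| 10% / 5% | 1.0 | 0.0 | 0.0 | 0.05 | 93% |
| 20% / 10% | 2.0 | 0.0 | 0.0 | 0.5 | 70% |
| 30% / 15% | 3.0 | 0.0 | 0.0 | 1.4 | 51% |
| 30% / 20% | 2.0 | 0.0 | 0.0 | 1.2 | 40% |

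The zeros follow from setting hospital stay equal in the two arms, and the deletion column assumes that no facility patient's home date is captured. The table shows how the rules act. It is not an estimate for this trial.

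**The case against.** The case against has several parts, and some of it stands.

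- **The home-versus-facility contrast is measured elsewhere.** This stands. A reader might infer that the plan cannot detect a block that sends more patients home. Section 4.1 assesses discharge placement in its own right, so such a difference could appear there. What is at risk is the comparison of time to home.
- **The plan does not say that facility patients are coded as missing or dated at transfer.** This also stands. A reader might infer that only patients who went straight home are compared, or that transfers count as early returns. Neither is written. Home discharge can be read as the day the patient gets home, and a patient home on day 17 then has the value 17. But that value still meets the 2 SD rule, and a patient not home at last contact still has no value.
- **The mixed model is not the source of the bias.** With one row per patient it reduces to ordinary regression. Section 5.1 also allows transformations and non-parametric methods as needed, but neither supplies a rule for patients not yet home.
- **Disposition may not be lost with a missed visit.** A late visit is a sensible time to ask about it, withdrawn patients are asked to attend Follow-Up Visit 2, and the chart may hold the information. The documents do not show that it would be lost.
- **The illustration is assumed and the outcome is not powered.** This is correct. With 25% against 15%, the standard error is √(0.25 × 0.75/40 + 0.15 × 0.85/160) = 0.074, and power is about Φ(0.10/0.074 − 1.96) = Φ(−0.61), or 27%. The eligibility limits on walking, BMI and ASA class may also keep facility discharge uncommon. Low power does not excuse a rule that removes patients because of their outcome, and in Step 2 a low facility share makes flagging more likely.

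**Conclusion.** The point holds for time to home. As written, the deletion rule removes patients not home at last contact, and the 2 SD rule tends to remove those who get home late. Both select on the outcome and can bias the comparison between arms.

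The size cannot be stated from the documents, which give neither a facility rate nor a delay. Under the assumptions shown, true differences of 1 to 3 days fell to 0 when facility patients were deleted or dated at transfer, and to between 0.05 and 1.4 days under the 2 SD rule alone.

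The consequence is limited to one exploratory outcome. The primary comparison of 24-hour SF-MPQ pain is unaffected. It should still be corrected, because the problem lies in rules that the plan states and a standard replacement is cheap.

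**What to change.** Amend section 5.1 before unblinding:

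- Define the endpoint as days from surgery to first arrival home, with time in a facility counted as not home.
- Exempt it from the missing-value deletion and +/- 2 SD rules.
- Take it out of the longitudinal model. Describe it with Kaplan-Meier or cumulative incidence curves, and compare arms by a log-rank test or Cox model that accounts for the randomisation strata (procedure, age, diabetes).
- Censor patients not home at the date of last contact, since Follow-Up Visit 2 has no fixed day. Treat death before arrival home as a competing event.
- Take disposition and its date from the chart at discharge, and confirm the home date at the existing Follow-Up Visits 1 and 2.

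The cost is SAP wording and one extra date field. No visit is added.

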1.0 Specific Aims

Specific Aim

To compare the pain relief effects of plain bupivacaine nerve blocks against the effects of a 4-drug nerve block (bupivacaine-clonidine-buprenorphine-dexamethasone) for total knee or hip arthroplasty (TKA/THA). The survey instrument for the specific aim of the research (Short-Form McGill Pain Questionnaire, version 2, at 24 hr after surgery), is robust, valid, and reliable for evaluation of this important patient-centered quality-of-care parameter.

Exploratory Aims:

The secondary aims of short- and long-term physical therapy and rehabilitation-related benefits will also be examined for effects of nerve block drug treatment (plain bupivacaine versus 4-drug blocks) and surgical site (TKA/THA). The tertiary aim is to determine differences in opioid-related side effects based on nerve block treatment. Optimizing the described aims (ensuring that sufficient nerve block pain management duration does not compromise short- and long-term physical therapy efforts) is what we forecast that this comparative study will provide for future hypothesis generation, including the possibility that the 4-drug nerve block concept is adopted into general clinical practice.

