2.2 Preliminary Studies

Since July 2011, our center (VA Pittsburgh Healthcare System) has routinely used MMPNA with CBD (with bupivacaine) for its peripheral nerve blocks postoperative analgesia (in addition to the intraoperative spinal anesthetic for reliable surgical anesthesia). We have since published our observed outcomes for these patients (*Pain Medicine* 2015, ref.9), which was a median analgesic duration of 37 hr (95% confidence interval of the mean being 30-49 hr).

The duration of nerve block analgesia (as opposed to “numbness” or motor block) is important since longer duration appears to attenuate patient’s “rebound pain”⁽¹¹⁾. Since CBD are “motor sparing” analgesic adjuvants to local anesthetics used in nerve blocks, CBD added to bupivacaine will help extend the duration of analgesia, but would not necessarily prolong motor block. We anticipate that higher rebound pain scores will inhibit the achievement of postoperative PT/OT objectives.

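### The return-to-home model adjusts for pain, side-effects and general health that the block may itself change, so its MMPNA coefficient is not the total effect on days to home discharge

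*Combined protocol and SAP*

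**What the plan says.** The exploratory-aims paragraph of section 5.1 (Analysis Plan) announces a mixed model and states its purpose: "This procedure will test for nerve block type and surgical site effects, as well as an interaction between them". The return-to-home outcome follows: "Number of days from the joint replacement procedure" to discharge home. The next sentences name the SF-MPQ-2 for pain responses, then "use of postoperative opioids with additional measurement by the Opioid-Related Symptom Distress Scale will also be assessed", then the SF-8 and SF-36 for general health. The paragraph closes with the covariate rule: "Measures of pain, analgesic side-effects, and general health status will be covariates included in the modeling of the effect of MMPNA on return-to-home".

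The general covariate list earlier in section 5.1 follows a statement that all hypotheses and aims will be tested by this modelling, and it is not limited to one endpoint. Besides baseline variables it includes "concurrent general health status (e.g., daily SF-8, subsequent SF-36, and WOMAC").

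Elsewhere the protocol treats the same quantities as results of the block. The primary hypothesis is "of an improvement in pain (measured by the SF-MPQ- version 2) 24 hr after surgery during in-hospital recovery". Section 1.0 states: "The tertiary aim is to determine differences in opioid-related side effects based on nerve block treatment". Section 2.2 adds: "We anticipate that higher rebound pain scores will inhibit the achievement of postoperative PT/OT objectives".

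No return-to-home model without these covariates is described, and nothing labels the analysis as mediation or as a direct effect.

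**The concern.** The named target is the effect of the 4-drug block on return home. Randomisation identifies that total effect when the model holds only treatment, site and variables fixed before the block. Once the model also holds variables that the block can change, two things happen.

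- **The hypothesis changes.** The null for the MMPNA coefficient becomes no effect other than through pain, side-effects and general health. A benefit that comes from better pain relief, which is the trial's main idea, is removed from the coefficient.
- **Protection from confounding is lost.** If frailty or disease severity drives both postoperative pain and length of stay, holding pain fixed ties treatment to that unmeasured factor. The coefficient is then biased even as a direct effect, and it can point towards delay when there is none.

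At stake is how the return-to-home result is read: a real benefit could be reported as absent, or a neutral block could be reported as slowing discharge.

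**Working it through.** **Plan's own figure.** There is none. The sample-size section (5.6) concerns block duration only. The documents give no SD, effect size or pain–stay correlation for days to home discharge, so every effect size below is an assumption.

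**Inputs.**
- From the documents: 40 control and 160 MMPNA patients (20 and 80 per procedure, section 4.1), and two-sided 0.05 (stated in 5.6 for the sample size).
- Assumed: a continuous outcome; pain with within-arm SD 1; MMPNA lowers pain by d SD (0.5 or 1).
- Common factor: k = √(1/40 + 1/160) = 0.1768.

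**Case A: the whole effect runs through pain.** Stay = g × pain + error, with residual SD 1. The total effect is −d·g.

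Without pain in the model, SE = k·√(1 + g²). For d = 1:

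| g | Effect size | SE | Effect/SE | Power |
|---|---|---|---|---|
| 0.4 | 0.40 | 0.190 | 2.10 | 55% |
| 0.6 | 0.60 | 0.206 | 2.91 | 83% |
| 0.8 | 0.80 | 0.226 | 3.53 | 94% |

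A simulation of 4,000 trials per case gave 56%, 83% and 95%. For d = 0.5 it gave 18%, 32% and 42%.

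With pain in the model, the expected MMPNA coefficient is 0, so the test rejects about 5% of the time in every row.

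The slopes g are per SD of pain on a scale where the residual SD of stay is 1. Dividing by √(1 + g²) gives 0.37, 0.51 and 0.62 in within-arm SDs of stay.

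**Case B: no effect on stay, but a shared cause.** Within-arm pain–stay correlation is r, both SDs are 1, and MMPNA lowers pain by d.

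- Adjusted MMPNA coefficient = +r·d, towards longer stay.
- R² of treatment with pain = 0.16d²/(1 + 0.16d²), where 0.16 = 0.2 × 0.8.
- SE = k·√(1 − r²)/√(1 − R²).
- r = 0.3, d = 1: coefficient +0.30, R² = 0.138, SE = 0.182, ratio 1.65, rejection about 38% (simulation 36%).
- r = 0.3, d = 0.5: coefficient +0.15, SE = 0.172, ratio 0.87, rejection about 14%.
- Without the pain covariate, rejection is about 5%.

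**Case C: a real shortening plus a shared cause.** A further simulation (2,000 trials per case) used d = 0.5 to 1.0, slopes 0.3 to 0.7, and an unmeasured factor with loading 0.5 on both pain and stay. The true total effect was −0.15 to −0.70. The adjusted coefficient was about 0.5² × d, that is +0.12 to +0.25, and it was significant in 8% to 23% of trials.

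**Weak links.**
- Case A with d = 0.5, g = 0.2: ratio 0.10/0.180 = 0.55, power about 9% without pain and 5% with it, a loss of about 4 points.
- Case B with d = 0.5, r = 0.1: ratio 0.05/0.179 = 0.28, rejection about 6%.

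Side-effects and general health were not simulated. The same reasoning applies to any post-block measure that the block affects.

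**The case against.** **Timing is inferred.** The covariate sentence gives no time point, and in the preceding text the word postoperative qualifies opioid use, not pain. The study calendar (Appendix 1) has SF-MPQ-2 and ORSDS at baseline too. This stands: post-block values are the natural reading, given the sentences before it and the concurrent measures in the general list, but it remains a reading. Opioid use itself is not among the covariates named.

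**The mechanism is partly indirect.** Section 2.2 speaks of PT/OT objectives, not of discharge, and section 4.4 measures rebound pain with the DVPRS, not the SF-MPQ-2. Section 2.1 names a route other than pain: numbness and weakness delaying therapy. So the benefit need not run wholly through pain, and a direct effect could be of interest. It is not, however, the effect that the plan names.

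**The illustration is idealised.** Stay is typically 2 to 5 days (section 4.1), a short day count and not a normal variable, and the large distortions need a strong pain effect and a sizeable pain–stay link.

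**Stronger readings.** A reader might infer that the model must give a wrong answer whatever the truth. The documents do not support that; with weak links the distortion is minor. A reader might also infer that this sentence undermines the trial's main result. It does not: it concerns return-to-home only, among aims that section 1.0 frames as hypothesis-generating. Finally, a reader might take the general covariate list to apply only to the 24-hour pain model, so that one edited sentence would suffice. That list covers all aims.

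**Conclusion.** The point holds for the return-to-home analysis as described. On the natural reading of section 5.1, the MMPNA coefficient does not estimate the total effect on days to home discharge. It omits whatever acts through pain, side-effects and general health, and it is biased if an unmeasured factor drives both pain and stay.

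That conclusion about what is estimated rests on the text. The size does not: under the stated assumptions it runs from a loss of about 4 points of power to nearly all of it, and from about 6% to about 38% false rejection towards delay. If baseline values were meant for every one of these covariates, the problem disappears, but the plan has to say so, and the concurrent measures in the general list contradict that reading for general health. The issue is worth correcting because the correction is cheap; its reach is one exploratory endpoint.

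**What to change.** Two edits in section 5.1:

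1. **Exploratory-aims paragraph.** Replace the covariate sentence. Estimate the MMPNA effect on days to home discharge from treatment, surgical site, their interaction and pre-block covariates only: age, diabetes status, gender, weight, smoking status, and baseline SF-36, WOMAC, SF-MPQ-2 and ORSDS.
2. **General covariate list.** State that concurrent SF-8, subsequent SF-36 and subsequent WOMAC are not used in the return-to-home model. Without this, the first edit would leave post-block health measures in place.

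If the team wants to know how much of any effect runs through pain, side-effects or general health, report that version separately as a mediation analysis. It should name the time point of each postoperative covariate, state the assumption of no unmeasured common cause of covariate and stay, and not be read as the MMPNA effect.

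The cost is a text change before unblinding. All the replacement covariates are already collected before the block (section 4.3 and Appendix 1), so no new data, visits or patients are needed.
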